**B1. PURPOSE OF PROTOCOL**

**Hypothesis**

1. Pre-treatment with a buffered lidocaine solution provides superior pain control compared to a standard lidocaine procedure before intradetrusor botox injection

**Primary Objectives:**

1. Procedural pain associated with intradetrusor botox injections on a standardized Visual Analogue Scale

**Secondary Objectives:**

1. Patient satisfaction measured on a five point Likert scale
2. Willingness to undergo procedure again measured on a five point Likert scale
3. Adverse events
4. Demographic and clinical factors that predict high pain scores during the procedure

**B2. SIGNIFICANCE AND BACKGROUND FOR THE STUDY**

Lidocaine is a commonly used amide-type local anesthetic. Lidocaine exists as both a quaternary water soluble structure, and a tertiary lipid-soluble structure. Only the tertiary lipid-soluble structure can cross the lipid bilayer of a cell membrane and thereby enter a neurons axoplasm and induce the desired effect. The ionization constant of lidocaine is 7.7 which means that at a pH of 7.7, 50% of lidocaine is available in the tertiary lipid-soluble structure. At a physiologic pH between 7.35 and 7.45 only around 44% of lidocaine is in the tertiary lipid-soluble structure. However, for lidocaine to be stable in solution, it is typically formulated as a hydrochloride salt and the pH of most commercially available lidocaine solutions are at a pH of 6.09. In an acidic solution the majority of lidocaine is available in the quaternary water-soluble structure and at this pH only 2.5% of lidocaine is in the tertiary lipid-soluble structure. A Cochrane review found that increasing the pH of lidocaine prior to injection decreased pain and increased patient satisfaction perhaps because of the aforementioned pharmacokinetic principles

Lidocaine is typically used as anesthetic for intradetrusor injections of onabotulinum toxin A for the treatment of refractory overactive bladder. In 2003, a technique for intradetrusor injections of onabotulinum toxin A was first described using only local anesthesia. At that time, the procedure involved intrauterthral lidocaine. The procedure has evolved since that time and currently many physicians utilize protocols with both

utraurethral and intravesical lidocaine. At baseline intradetrusor onabotulinum toxin A injections are generally well tolerated and with reported mean VAS scores around 3.

For patients with refractory overactive bladder, the standard of care is intradetrusor onabotulinum toxin A injections. In our clinical practice, the standard of care is to empty the bladder then retrograde fill the bladder with a 1:1 mixture of 1% lidocaine normal saline. This solution remains in the bladder for approximately 15 minutes prior to injection. Given that urine is typically acidic and commercially available lidocaine solutions are similarly acidic, it is likely that only a fraction of intravesical lidocaine is in the active tertiary lipid-soluble form. The goal of this study is to determine if we can improve the procedural pain of intradetrusor onabotulinum toxin A injections using a buffered solution compared to our standard solution.

### B3. DESCRIPTION OF RESEARCH PROTOCOL

#### A. Study Design – Overview, Methods, Procedures

**Brief overview:** This will be a prospective double-blinded randomized controlled trial comparing two pre-treatment protocols for patients undergoing intradetrusor botox injections to determine if a buffered lidocaine solution offers superior pain control.

**Study Protocol:** After approval by the IRB, providers will approach possible participants who are having intradetrusor botox injection for overactive bladder which is the standard of care for patients with refractory overactive bladder. If the patient meets eligibility criteria, consent forms will be signed and the patient will be randomized 1:1 to receive either our standard pretreatment regimen with 50 mL 1% lidocaine + 50ml of 0.9% normal saline or our buffered bicarbonate protocol with 50 mL 1% lidocaine + 45ml of 0.9% normal saline + 5 mL 8.4% sodium bicarbonate. The primary end point of this trial is to assess the pain scores measured on a Visual Analogue Scale (VAS) immediately following the procedure. Secondary end points include patient satisfaction, willingness to undergo repeat treatment and adverse events.

All subjects will be randomized 1:1 at the first intervention visit to one of the two protocols . At the completion of the procedure, patients will be asked to complete a brief questionnaire about their experience. Patients will follow up in clinic for a post-void residual check two weeks after the procedure as is standard for

MOUNT AUBURN  
HOSPITAL

### Methods:

Standard protocol: 50 mL 1% lidocaine + 50ml of 0.9% normal saline

Bicarbonate protocol: 50 mL 1% lidocaine + 45ml of 0.9% normal saline + 5 mL 8.4% sodium bicarbonate

### Inclusion criteria:

Female patient

Primary diagnosis of overactive bladder

### Exclusion criteria:

Neurogenic bladder

Urinary retention

### Outcome Measures:

The **primary** outcomes measures will include:

- Pain: The Visual Analogue Scale (VAS) consists of a straight line with the endpoints defining extreme limits such as 'no pain at all' and 'pain as bad as it could be' which was first described in 1923. The patient is asked to mark his pain level on the line between the two endpoints. The distance between 'no pain at all' and the mark then defines the subject's pain. Studies vary on the definition of a clinically meaningful change in pain, but suggest that a difference of anywhere from 12% to 38% may be clinically significant

The **secondary** outcomes measures will include

- Satisfaction
- Willingness to undergo repeat procedure
- Adverse events
  - Adverse events will be collected from the medical record and include postoperative urinary tract infections, hematuria, readmission, urinary retention, number of patient phone calls
- Pelvic Floor Distress Inventory (PFDI-20) Scores
  - The short-form version of the Pelvic Floor Distress Inventory has a total of 20 questions and 3 scales (Urinary Distress Inventory, Pelvic Organ Prolapse Distress Inventory, and Colorectal-Anal Distress Inventory). Total PFDI score measured on a 0-300 scale with higher scores equal to greater pelvic floor distress. As with the Total PFDI Score, higher subscale scores equal greater pelvic floor distress, on a 0-100 scale

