### **B5. POSSIBLE RISKS AND ANALYSIS OF RISK/BENEFIT RATIO**

Possible risks include the potential loss of confidentiality. This risk will be minimized by the following methods. All patient data will be made anonymous and linked with a subject ID which will be stored separately from the data in locked cabinets and on a password protected drive behind the MAH firewall. Once the surveys are complete, the data will be completely deidentified and the master code linking the direct identifier to the dataset will be destroyed. Other potential risks include bladder pain, hematuria, urinary retention, urinary tract infections. These risks are all standard risks associated with cystoscopy and intradetrusor botox and should not be different between protocols. To date there have been no adverse events reported with the use of a buffered lidocaine solution for bladder instillations. In theory, buffering of the solution with sodium bicarbonate may cause precipitation of the dissolved lidocaine and thereby decrease efficacy, but in clinical practice this has not been demonstrated and studies looking at buffered lidocaine for injection found improved pain scores suggesting increased efficacy.

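### Adverse events are taken passively from the chart, with no listed reaction to the instilled solution and no bladder pain, so the objective is poorly suited to describing harm from buffering

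*Combined protocol and SAP*

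**What the plan says.** The Secondary Objectives in B1 include "Adverse events", and the study overview in B3.A repeats them as a secondary end point. Outcome Measures gives the only description of how they are gathered: "Adverse events will be collected from the medical record and include postoperative urinary tract infections, hematuria, readmission, urinary retention, number of patient phone calls". No time window is stated.

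Section B5 has its own list: "Other potential risks include bladder pain, hematuria, urinary retention, urinary tract infections". It continues: "These risks are all standard risks associated with cystoscopy and intradetrusor botox and should not be different between protocols". On the buffered solution it reports: "To date there have been no adverse events reported with the use of a buffered lidocaine solution for bladder instillations". The one buffer-specific concern it raises is that "buffering of the solution with sodium bicarbonate may cause precipitation of the dissolved lidocaine and thereby decrease efficacy", which is a loss of effect rather than a harm.

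The Methods paragraph shows that the arms differ in one respect: 5 mL of saline is replaced by 5 mL of 8.4% sodium bicarbonate. The Study Protocol paragraph provides a VAS pain score straight after the procedure, a brief questionnaire at its completion, and a clinic visit at two weeks for a post-void residual check.

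**The concern.** Any harm specific to one arm must come from the instilled solution, but none of the named adverse events is a reaction to it. Three are clinical diagnoses that B5 attributes to cystoscopy and botox. The other two, readmission and number of phone calls, are nonspecific contacts. B5 also names a fourth clinical risk, bladder pain, which the Outcome Measures list leaves out.

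Collection is passive as well. A transient symptom enters the medical record only if the patient mentions it and someone writes it down. The background section rests on the premise that "Only the tertiary lipid-soluble structure can cross the lipid bilayer of a cell membrane" and that a higher pH puts more of the drug into that form. The same reasoning makes it sensible to ask about local or absorption-related symptoms, although the plan names no such risk.

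At stake is how the safety result will be read. A report of no difference in adverse events would tend to be taken as support for the buffered solution, when the symptoms most closely tied to it had not been systematically sought.

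**Working it through.** **1. The two lists side by side**

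| Item | Listed in Outcome Measures | Named as a risk in B5 and expected equal by arm |
|---|---|---|
| Urinary tract infection | yes | yes |
| Hematuria | yes | yes |
| Urinary retention | yes | yes |
| Readmission | yes | no |
| Number of phone calls | yes | no |
| Bladder pain | no | yes |
| Reaction to the instilled solution | no | no |

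The bladder pain row is an internal mismatch that needs no assumption. The last row is a gap in both places. The expectation of equal risk covers three of the five listed events, and it covers bladder pain too.

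**2. What the same-day measurements cover**

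The VAS is a single patient-reported score in both blinded arms, taken after instillation and injections are complete. It would reflect irritation felt by then, mixed with injection pain. It does not cover bladder pain that develops later or symptoms other than pain. The content of the questionnaire is described only as concerning the patient's experience.

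**3. The plan's sample size**

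Inputs from Sample size and Statistical Considerations: difference 1.4, SD 2.08, two-sided alpha 0.05, power 0.80, 1:1 allocation.

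Normal approximation: n = 2 × (1.960 + 0.842)² × (2.08/1.4)² = 34.7, so 35 per arm. The two-sample t-test gives 35.6, so 36 per arm. The stated figure reproduces. It is sized for pain; no calculation is given for adverse events.

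**4. Chance of recording no event among 36 buffered-arm patients**

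Assume a true symptom rate of 10% (the documents give none) and let c be the fraction of cases recorded. Then P(none) = (1 − 0.10c)^36.

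| Capture | Calculation | P(none recorded) |
|---|---|---|
| 20% from charts | 0.98^36 | 48% |
| 50% from charts | 0.95^36 | 16% |
| 80% from charts | 0.92^36 | 5% |
| 100%, every patient asked | 0.90^36 | 2% |

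The last row assumes that every affected patient reports the symptom when asked.

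**5. What 36 per arm can show by arm**

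Two-sided Fisher test at 0.05, with assumed rates and full capture:

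- 10% versus 0%: significance needs at least 6 events against 0 (6 v 0 gives p = 0.025; 5 v 0 gives p = 0.054). P(6 or more of 36 at 10%) is about 15%.
- 5% versus 10%: power 0.03.
- 5% versus 15%: power 0.15.
- 5% versus 20%: power 0.35.
- 5% versus 30%: power 0.76.
- 10% versus 40%: power 0.80.

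With 0 events in 36, the one-sided 95% upper limit is 1 − 0.05^(1/36) = 8.0%. The upper end of a two-sided 95% interval is 1 − 0.025^(1/36) = 9.7%.

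Better capture therefore improves the description of what happens in each arm. It does not give the trial the power to detect a moderate excess.

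**The case against.** The strongest reply is that the trial already asks about the most plausible harm. If buffering irritated the bladder during the procedure, the immediate VAS, in randomised and blinded arms, is where that would appear. This stands for immediate pain, but not for attributing it to the solution, for later bladder pain or for non-pain symptoms.

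Second, the adverse-event list is introduced by a word that leaves it open, no window is stated, and same-day procedure notes belong to the medical record. This also stands. A reader might infer that events come only from later records, but the text does not say so. What remains is that collection is passive.

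Third, a reader might infer that the objective cannot detect harm, or that a null result is built in, because B5 says the risks "cystoscopy and intradetrusor botox and should not be different between protocols". That inference fails. B5 states an expectation, and a randomised comparison could still show a difference. The expectation does not reach readmission or phone calls, either of which could pick up troublesome symptoms after the patient leaves. Nor can it be used to discount infection, hematuria and retention while treating bladder pain as informative, since bladder pain is under the same statement. The case for collecting bladder pain is simply that the plan names it as a risk and does not list it.

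Fourth, B5 reports no adverse events to date with buffered instillations, and absorption symptoms are not a risk the plan names. Both are true, and both limit how serious the point is. The absence of reports is nevertheless something a blinded comparison could check if patients were asked.

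Finally, the questionnaire itself is not shown and the follow-up description breaks off in the text available for this review, so safety questions there cannot be ruled out.

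**Conclusion.** The point holds in a limited form. The adverse-event objective relies on passive chart collection, lists no reaction to the one thing that differs between arms, and omits a risk that the plan itself names. It is poorly suited to describing harm from the buffered solution, and a finding of no difference would be weak evidence of safety.

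The mismatch over bladder pain and the missing instillation reactions rest on the text alone. The size of the capture problem rests on assumptions: at a 10% symptom rate, the chance of recording nothing in 36 patients runs from about 48% to 5% as chart capture rises from 20% to 80%, against 2% with complete ascertainment. Even then, only a large excess would be shown reliably by arm.

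A reader might take the background figures, 2.5% lipid-soluble at pH 6.09 and around 44% at physiologic pH, as the difference in exposure between the arms. They are not: the documents give no pH for either instilled mixture, and the fractions say nothing about symptom risk.

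**What to change.** - Under Outcome Measures, add bladder pain or burning after instillation and a short yes/no symptom checklist as adverse events. Ask every patient in both arms on the existing end-of-procedure questionnaire.
- Ask about bladder pain since the procedure at the existing two-week visit.
- State the collection window for events taken from the medical record.
- Report the solicited items by arm with confidence intervals, separately from the cystoscopy and botox events. State in advance that no difference will not be read as showing safety, because 36 per arm can reliably show only a large excess.
- Align the B5 risk list with Outcome Measures, so that bladder pain appears in both and the expectation of equal risk is confined to the cystoscopy and botox events.

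The cost is a few items on a form already given and one question at a visit already held, plus more minor events to report. Treatment, visits and sample size do not change.

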### Sample size:

We are planning a study of a continuous response variable from independent controls and experimental subjects with one control per experimental subject. In a prior study looking at pain associated with intradetrusor botox, the response within each group had a standard deviation of 2.08. If the true difference between the experimental and control groups is 1.4 which would represent a 38% difference in pain scores, then we would need to enroll 36 controls and 36 experimental subjects to reject the null hypothesis that the population means of the experimental and control groups are equal with a probability (power) of 0.8. The type 1 error probability associated with this test of this null hypothesis is 0.05.

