**Data collection:**

Baseline characteristics collected from the medical records and collected as part of routine clinical care for every patient:

- Age (years),
- Gravid (numeric value),
- Para (numeric value),
- BMI (height and weight)
- Race/ethnicity
- Medical history (fibromyalgia, use of chronic pain medications, chronic back pain)
- Surgical history (hysterectomy, prolapse surgery, urinary incontinence surgery)
- Pre-treatment Kegel strength
- Pre-treatment myofascial pain
- Pre-treatment POPQ
- Pre-treatment PFDI-20

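### Is PFDI-20 a secondary outcome that the trial measures only at baseline?

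*Combined protocol and SAP*

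**What the plan says.** Outcome Measures (section B3.A) names "Pelvic Floor Distress Inventory (PFDI-20) Scores" as a secondary outcome. It describes a total on a 0-300 scale and three subscales on 0-100 scales. It gives no assessment time, change score or comparison between arms.

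Data collection lists "Pre-treatment PFDI-20". The list is introduced as "Baseline characteristics collected from the medical records and collected as part of routine clinical care for every patient".

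The design overview states: "Secondary end points include patient satisfaction, willingness to undergo repeat treatment and adverse events". PFDI-20 is not named there, nor among the four secondary objectives in section B1. The fourth of those objectives is "Demographic and clinical factors that predict high pain scores during the procedure".

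After treatment, the overview describes a VAS immediately after the procedure and a short form: "At the completion of the procedure, patients will be asked to complete a brief questionnaire about their experience". It then turns to follow-up: "Patients will follow up in clinic for a post-void residual check two weeks after the procedure as is standard for". The available text stops there, in mid-sentence.

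Statistical Considerations (section B3.B) covers descriptive statistics, risk ratios for pre-specified risk factors and a general two-sided 0.05 threshold. It does not mention PFDI-20.

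**The concern.** An outcome has to be measured after the intervention. If PFDI-20 is taken only beforehand, any difference between randomised arms is chance, and a test of it says nothing about buffered lidocaine. Section B3.B applies one 0.05 threshold to all tests and mentions no multiplicity control. Someone working through the outcome list literally could therefore compare the total and the three subscales between arms and report a chance imbalance as a secondary finding. The score's proper use, as a baseline descriptor or a candidate predictor of pain, might also be overlooked. The disagreement between the outcome list, the objectives and the end points makes the doubt reasonable.

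**Working it through.** **1. Does the point touch the plan's own figure?** The inputs are in Sample size (section B3.A): difference 1.4, "the response within each group had a standard deviation of 2.08", power 0.8, type 1 error 0.05, equal allocation. Section B3.B makes the tests two-sided.

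- Normal approximation: n per arm = 2 × (1.96 + 0.842)² × 2.08² / 1.4² = 2 × 7.85 × 4.326 / 1.96 ≈ 34.7, which rounds up to 35.
- Two-sample t-test: 35.6, which rounds up to 36 and matches the stated 36 per arm. Power at 36 per arm is 0.804.

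The figure reproduces. It concerns VAS pain only, and PFDI-20 does not enter it.

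**2. Is PFDI-20 shown to be collected only before treatment?** Each source, read in turn:

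| Place | Timing given for PFDI-20 | Can it settle the question? |
|---|---|---|
| Outcome Measures | None | No |
| Data collection | Pre-treatment | No. It is a baseline list, not a visit schedule; VAS, satisfaction and willingness are absent from it too |
| Overview, end-of-procedure form | Not named | In part. The form concerns the patient's experience |
| Overview, two-week visit | Not named | No. The sentence breaks off in the available copy |

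The supportable statement is that no readable text gives a post-treatment PFDI-20. That is weaker than saying none is planned.

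**3. Does the plan prescribe a between-arm test of it?** No. Outcome Measures gives scale ranges, and section B3.B gives general methods without naming the instrument. The 0.05 threshold says how to read tests that are done. It does not say that this one will be done.

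**4. How large would the risk be if such tests were added?** Four null comparisons (total plus three subscales), if independent, give 1 − 0.95⁴ = 1 − 0.8145 = 0.185. They cannot be independent if the total is the sum of the subscales, and the ranges fit that reading (3 × 100 = 300). Three independent subscales alone give 1 − 0.95³ = 1 − 0.8574 = 0.143. Under perfect correlation the figure is 0.05. The range is thus 5% to 18.5%, all of it conditional on tests that the plan does not state.

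**5. What happens if the plan is followed with the baseline score alone?** It is tabulated with the other baseline characteristics, or it enters the search for predictors of pain under the fourth secondary objective, for which section B3.B already provides risk ratios. Neither use gives a wrong answer.

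**The case for a change.** The strongest case for a change is that an outcome with neither a time point nor an analysis is undefined, which leaves room for choices after the data are seen. The secondary objectives, and the sentence listing the end points, can be read in full and omit PFDI-20, so the lists fail to match whatever the missing follow-up text says. The repair would also be cheap: move the item to the baseline characteristics, or state a later time point.

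Part of this stands. The lists are inconsistent, and a tidier protocol would have reconciled them. The end-point sentence is not a closed list, however: it says which end points are included, and it also leaves out the fourth secondary objective. Omission from it does not show that PFDI-20 cannot be measured. The harm described depends on an analysis that the documents do not contain, and the baseline role that would be assigned to the score is already assigned under Data collection. If a later PFDI-20 was intended, stating its time would complete the record of a minor outcome. The arms differ only in the bladder instillate, and the documents give no reason to expect that difference to alter pelvic floor symptoms.

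**Conclusion.** No change follows. The observation is accurate in a narrow form: PFDI-20 is called a secondary outcome, its only readable collection point is pre-treatment, and no objective, listed end point or analysis names it. This is a gap in detail that a competent analyst fills correctly, by describing the score at baseline and, if wanted, using it as a candidate predictor. Relabelling it would alter no result or conclusion. The effect on the primary VAS comparison, the 36 per arm and the other secondary outcomes is nil.

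The conclusion rests on two assumptions. One is that analysts do not test a pre-treatment score between arms and present the result as a treatment effect; nothing in the documents tells them to. The other is that the unavailable follow-up text holds no conflicting PFDI-20 instruction. If it holds a post-treatment assessment, the premise of the concern falls away.
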